ANALYTIC PLAN FOR PROTOCOL A Pilot Study of Hypertension Management Using Remote Patient Monitoring Study 1

PRINCIPAL INVESTIGATOR:

[name], MPH
Professor of Medicine, Division of General Internal Medicine & Geriatrics
Director, Center for Primary Care Innovation
[contact]
Email Address: [contact]

VERSION DATE: 1/26/21

Start date 11/19/2020

Define primary study cohort as of this date

Define secondary study cohort as of this date

Define matched control cohort as of this date (attempt to match pilot to control at rate of 4:1 for primary and 2:1 for secondary)

Groups of interest:

- Patients meeting **primary patient population** criteria at the study start date
 - Adults aged 65 to 85 years at the time of the study start date AND
 - One or more office or telehealth visits in the year preceding the study start date at the eligible NM primary care sites AND
 - Medicare or Medicare Advantage insurance on study start date AND
 - Last two office blood pressures elevated (either ≥ 140 mmHg systolic or ≥ 90 mmHg diastolic) in the past 2 years AND
 - Diagnosis of hypertension in the year preceding the study start date (problem list or encounter diagnosis : all of the subcodes of I10, I11, I12, I13, I15) AND
 - Not meet the exclusion criteria
 - Persistent atrial fibrillation as indicated in the EHR
 - Exclude if “permanent atrial fibrillation or persistent atrial fibrillation” [I48.1, I48.2] (active problem list or two encounter diagnoses in past 2 years)
 - Stage IV or more severe kidney disease, defined as the most recent estimated glomerular filtration rate < 30 per $1.73m^2$ or currently on renal replacement therapy (i.e. hemodialysis or peritoneal dialysis) [N18.4, N18.5, N18.6]
 - Diagnosis of dementia as indicated in the electronic health record [all subcodes of F01-F03, all subcodes of G30, all subcodes of G31]
- Patients meeting **secondary patient population** criteria at the study start date
 - Meet criteria for primary population OR
 - Diagnosed hypertension but did not have the last two office blood pressures ≥ 140 mmHg systolic or ≥ 90 mmHg diastolic OR
 - No diagnosis of hypertension in the past year but did have the last office blood pressure ≥ 140 mmHg systolic or ≥ 90 mmHg diastolic

- Control group matched based on the primary study criteria
- Control group matched based on the secondary study criteria.

Matching criteria

- Sex
- Age (+/- 5 years)
- Mean SBP from T-365d to T-183d (+/- 10 mm Hg)
- Mean SBP from T-182d to T-0d (+/- 10 mm Hg)
- Number of office visits to primary care in the past year categories : 1, 2, 3-4, 5+

Assess for time 0 (11/19/2020)

Characteristics of study populations and matched control populations.

At time 0, 1 month (12/18/2020), 3 months (2/18/2020) and 6 months (5/18/2020) describe for each group:

- The proportion of patients who satisfy the performance measure Controlling High Blood Pressure (NQF 0018)
- The systolic blood pressure at the most recent face-to-face office visit

At time 1 month (12/18/2020), 3 months (2/18/2020) and 6 months (5/18/2020) describe for each group:

- Number of antihypertensive medication intensifications between the study start and the measure date

Hypothesis testing—perform separately for primary and secondary populations

H1: Antihypertensive medication intensification will be greater in pilot clinic(s) with RPM compared to contemporaneous control clinic(s).

Compare at 1, 3, and 6 months the number of medication intensifications between study group and control group using Poisson regression (if variance of medication intensifications is approximately equal to the mean) or otherwise negative binomial regression with study group as the independent variable.

H2: The proportion of patients who satisfy the performance measure Controlling High Blood Pressure (NQF 0018) will be greater in pilot clinic(s) with RPM compared to contemporaneous control clinic(s).

Compare at 1, 3, and 6 months the proportion of patients in the study group and control group who satisfy the performance measure Controlling High Blood Pressure (NQF 0018) using logistic regression with study group and baseline systolic blood pressure as independent variables.

H3: The systolic blood pressure at the most recent office visit will be lower in pilot clinic(s) with RPM compared to contemporaneous control clinic(s).

Compare at 1, 3, and 6 months the systolic blood pressure at the most recent face-to-face office visit among patients in the study group and control group using linear regression with study group and baseline systolic blood pressure as independent variables.

RPM enrolled patient analyses

We will explore the trajectories of blood pressure for individuals who are prescribed RPM.

We will describe all patients who are enrolled in RPM at their enrollment date and follow their blood pressure outcomes at 1, 3, and 6 months from their enrollment (or until the study end date).

We will retrospectively, at the end of the study end date, identify matched controls (4:1) for patients enrolled in RPM selected from patients in the non-pilot clinics and matched on the same baseline criteria (assessed at the time of RPM ordering). We will perform comparisons analogous to those described above for the primary cohort.

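### Matching ratios are only attempted and all controls are pooled with equal weight, so unequal set sizes can bias the estimates, H1's most of all

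*SAP*

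**What the plan says.** The cohort definitions at the start of the SAP say to "attempt to match pilot to control at rate of 4:1 for primary and 2:1 for secondary". The list of matching criteria requires agreement on five items together: sex, age within 5 years, mean SBP within 10 mm Hg in each of two half-year windows, and one of four categories of primary care office visits. The SAP gives no minimum set size and no rule for a short or empty set.

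Under Hypothesis testing, H1 uses Poisson regression if the variance of the counts is close to their mean, "otherwise negative binomial regression with study group as the independent variable". H2 is tested "using logistic regression with study group and baseline systolic blood pressure as independent variables", and H3 "using linear regression with study group and baseline systolic blood pressure as independent variables". None of the three has a weight, a matched-set term or a conditional likelihood, so each control enters with weight one.

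The RPM-enrolled analysis specifies 4:1 controls, this time without saying that the ratio is only attempted, and uses comparisons analogous to those for the primary cohort.

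**The concern.** Matching balances the factors within each set. Pooling the sets keeps that balance only if every pilot patient brings the same number of controls. If some bring four and others one or two, the pooled controls over-represent the kinds of patient who were easy to match. Where ease of matching is related to outcome, the group comparison shifts even when every matched pair agrees perfectly.

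This concerns the point estimate. Correct standard errors for matched data would not remove it.

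Unequal sets are likely. Five joint criteria are demanding, and some features of the plan make shortfalls easy to foresee:

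- The primary population is defined by "Last two office blood pressures elevated (either ≥ 140 mmHg systolic or ≥ 90 mmHg diastolic) in the past 2 years", which tends to give a right-skewed SBP distribution with few candidates at the top.
- A patient with one visit in the year may have no SBP in one of the two windows.
- Telehealth visits alone satisfy the entry criterion, but the visit categories count office visits and start at 1.

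At stake is the balance on visit frequency, age and sex that the matching was meant to secure. Visit frequency matters most for H1, because a visit is an occasion to intensify treatment.

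**Working it through.** The SAP gives no sample size, pool size, event rate or expected set size, so there is no figure of its own to reproduce. Only the target ratios (4 and 2), the calipers and the model terms come from the document. All other inputs are assumptions. The true rate ratio is 1.00 throughout.

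**Closed form for H1.** With study group as the only term, the fitted rate ratio is the ratio of the two group means. Let a share h of pilot patients be hard to match and get m controls, while the rest get the full M. Let the hard group's intensification rate be k times that of the rest.

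- Pilot mean = (1−h) + hk
- Unweighted control mean = [(1−h)M + hmk] / [(1−h)M + hm]

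For M = 4, h = 20%, k = 2 and m = 3, the pilot mean is 0.8 + 0.4 = 1.2. The control mean is (3.2 + 1.2)/(3.2 + 0.6) = 4.4/3.8 = 1.158. The ratio is 1.036.

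| m (of 4) | hard-to-match share of controls (pilot 20%) | ratio, k = 2 | ratio, k = 0.5 |
|---|---|---|---|
| 3 | 15.8% | 1.036 | 0.977 |
| 2 | 11.1% | 1.080 | 0.953 |
| 1 | 5.9% | 1.133 | 0.927 |
| 0, pilot patients kept | 0% | 1.200 | 0.900 |

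At 2:1 with k = 2, the ratio is 1.080 for m = 1 and 1.200 for m = 0. With k = 1, or with every set full, there is no bias.

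With weight 1/(set size), the control mean becomes (1−h)·M·(1/M) + h·m·(1/m)·k = (1−h) + hk. This equals the pilot mean, so the ratio is exactly 1.00 for m ≥ 1.

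**Simulations with the SAP's calipers.** Each uses 200 pilot patients, matching without replacement up to 4:1.

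| Assumed setting | Unweighted | Weighted |
|---|---|---|
| A: pool 1000, pilot SBP +2 mm Hg and more visits | 1.04 | 1.006 |
| A: identical clinic populations | 1.013 | 1.003 |
| A: pool 2000 | 1.02 | 1.006 |
| A: pool 4000 | 1.008 | 1.004 |
| B: right-skewed SBP, same in both groups, pools 600-4000 | 1.020-1.027 | 0.997-1.010 |
| B: as above, pilot SBP +5 mm Hg | 1.051-1.081 | 1.029-1.033 |
| C: symmetric SBP, identical populations, pools 1000-10000 | 1.007-1.011 | 1.002-1.008 |

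- Setting A assumes SBP SD 13, correlation 0.6 between windows, and control visit shares of 25/30/30/15% (18/27/33/22% in the pilot group where shifted). Rates are multiplied by 1, 1.3, 1.6 and 2.0 across visit categories and by exp(0.02) per mm Hg.
- Setting B assumes visit shares of 25/25/30/20%, exp(0.03) per mm Hg and exp(0.15) per visit category. Unmatched pilot patients are dropped.
- In setting B, 44% to 98% of pilot patients received all four controls. At 2:1 the unweighted ratio was about 1.01 to 1.05.
- Settings A and B used 60 repetitions each and Monte Carlo error was not computed, so third decimals should not be compared.

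The part due to unequal set sizes is roughly unweighted divided by weighted. In the worst row of setting B (pool 600, +5 mm Hg) that is 1.081/1.029 = 1.051. The remaining 1.029 is imbalance inside the calipers, which weighting does not reach.

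**Opposite direction.** Take the same visit shares (25/30/30/15%) and multipliers as in setting A, ignore SBP, and suppose one-visit patients get 2 controls and all others 4.

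- Pilot mean = 0.25 + 0.39 + 0.48 + 0.30 = 1.42
- Control mean = (50×1 + 120×1.3 + 120×1.6 + 60×2.0)/350 = 518/350 = 1.48
- Ratio = 1.42/1.48 = 0.96

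**The case against.** A reader might infer that set sizes will certainly vary and that H1 is therefore biased in favour of RPM. The document does not support that. It does not say what happens on a shortfall; cutting everyone to a lower fixed ratio would be consistent with the text and would leave no bias from this source. Nor does it say who is hard to match. High-SBP or frequent attenders may be short of controls, which would push the H1 ratio up. One-visit patients may be short because an SBP window is empty, which would push it down, as the 0.96 example shows.

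The size is also modest against sampling error. With 200 pilot patients and 800 controls at an assumed 0.3 intensifications each, the Poisson standard error of the log rate ratio is √(1/60 + 1/240) = 0.14; at 0.5 each it is √(1/100 + 1/400) = 0.11. A 4% bias (log 1.04 = 0.039) is about 0.3 standard errors and takes a two-sided 5% test to about 6%.

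A reader might also take H2 and H3 to be shown biased. No bias was computed for either, and their adjustment for baseline SBP should remove much of the SBP part. They remain open to imbalance in visits, age and sex.

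The planned description of both groups at time 0 could reveal such imbalance, but it does not correct it.

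These points limit certainty, direction and size. They leave the mismatch between an attempted ratio and pooled, equally weighted models standing.

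**Conclusion.** The point holds as a risk that the plan leaves open. If set sizes vary and ease of matching is related to outcome, the H1-H3 models as written do not preserve the balance that the matching creates, and the estimates can be biased. H1 is the clearest case because it has no covariate.

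Under the assumed inputs, the H1 ratio with no RPM effect is typically about 1.01 to 1.04. It reaches 1.05 to 1.08 when pilot SBP is 5 mm Hg higher, though part of that is imbalance within calipers. It reaches 1.13 to 1.20 in the extreme closed-form cases with one control or none. It falls below 1 if the hard-to-match patients are intensified less. There is no bias from this source if all sets are full. The sign and the size cannot be settled from the SAP.

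The correction is cheap and should be specified before analysis.

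**What to change.** In H1-H3 and in the RPM-enrolled comparison, give each matched pilot patient weight 1 and each control weight 1/(number of controls in its set), and use robust variance. Adding the matching factors, including visit category, as covariates would also deal with residual imbalance within the calipers.

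State the rule for short and empty sets. Pilot patients with no control should be excluded from the matched comparison, because weighting cannot help them and keeping them gave the largest bias above. Report their number and characteristics, and the distribution of set sizes.

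The cost is one weight variable and a few lines of SAP text. Some precision is lost where set sizes differ widely, and the estimate then applies only to pilot patients who could be matched.

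### In the secondary population, hypertension diagnosis varies by construction but is neither matched on nor adjusted for; a pre-specified indicator is a low-cost safeguard

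*SAP*

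**What the plan says.** Under Groups of interest, the SAP builds the secondary population from three branches joined by OR:

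- Branch 1: "Meet criteria for primary population OR". The primary criteria include "Diagnosis of hypertension in the year preceding the study start date", so these patients are all diagnosed.
- Branch 2: "Diagnosed hypertension but did not have the last two office blood pressures" elevated. These patients are also diagnosed, but no look-back period is given.
- Branch 3: "No diagnosis of hypertension in the past year but did have the last office blood pressure" elevated. These patients are undiagnosed over a one-year look-back.

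Controls are sought by matching ("attempt to match pilot to control at rate of 4:1 for primary and 2:1 for secondary"). The Matching criteria are sex, age within 5 years, mean SBP in each of two half-year windows within 10 mm Hg, and a category for "Number of office visits to primary care in the past year". The SAP also says that one control group is matched on the basis of the secondary criteria.

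Under Hypothesis testing, H1 to H3 are run separately in the primary and secondary populations with the same models. H1 is a Poisson or negative binomial regression with study group as its only term. H2 (logistic) and H3 (linear) contain study group and baseline SBP. At time 0 the plan describes "Characteristics of study populations and matched control populations", without naming the characteristics.

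**The concern.** The comparison is between pilot and control clinics, and no randomisation is described. Diagnosis is read from the problem list or from encounter diagnoses, which clinics record themselves, so coding habits could shift the undiagnosed share from one clinic to another. The SAP makes diagnosis part of the definition of the secondary population and then does nothing to balance it or adjust for it.

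If the diagnosed share differs between pilot patients and matched controls, and diagnosed patients have a different outcome at the same blood pressure, part of the secondary contrast reflects case mix rather than RPM. Medication intensification plausibly depends on whether hypertension has been recognised, and H1 is the model with no covariate. The primary population is not affected, because diagnosis is constant there.

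**Working it through.** The SAP states no figure on this point, so there is none to reproduce. The check has three parts.

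**1. Does matching on SBP stand in for diagnosis?**

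Take the eight combinations of diagnosed in the past year (yes/no), last BP high (yes/no) and previous BP high (yes/no).

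- If branch 2 means that the last two readings were not both high, 6 of 8 are eligible. Diagnosed and undiagnosed patients are both admitted in two BP patterns: both readings high, and last high with previous normal.
- If branch 2 means that neither reading was high, 4 of 8 are eligible. The both-high pattern still admits both kinds of patient.

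Example: two women aged 72 have half-year mean SBPs of 146 and 142, last two readings of 146 then 142, and two visits. They agree on every matching variable and on baseline SBP. One is diagnosed (branch 1) and the other is not (branch 3), yet they are a permitted match under either reading. SBP does not replace diagnosis.

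**2. How large could the bias be?**

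All inputs are assumed and the true RPM effect is set to none. Let p and c be the undiagnosed shares in pilot and control, and d and u the outcomes in diagnosed and undiagnosed patients (at equal baseline SBP for H3).

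H1: unadjusted rate ratio = [(1-p)d + pu] / [(1-c)d + cu].

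| Intensifications per patient, d / u | p = 0.20, c = 0.30 | shares reversed | p = 0.25, c = 0.30 | shares reversed |
|---|---|---|---|---|
| 0.50 / 0.15 | 0.430/0.395 = 1.09 | 0.92 | 0.4125/0.395 = 1.04 | 0.96 |
| 0.50 / 0.30 | 0.460/0.440 = 1.05 | 0.96 | 0.450/0.440 = 1.02 | 0.98 |
| 0.30 / 0.50 | 0.340/0.360 = 0.94 | 1.06 | 0.350/0.360 = 0.97 | 1.03 |

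H3: bias = (p-c)(u-d). With a 5 mm Hg difference between undiagnosed and diagnosed patients, a 10-point imbalance gives 0.10 × 5 = 0.5 mm Hg and a 5-point imbalance gives 0.05 × 5 = 0.25 mm Hg, in either direction.

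More extreme assumptions give more. With 10% vs 30% undiagnosed and an undiagnosed rate 0.3 times the diagnosed rate, H1 is (0.90 + 0.10 × 0.3)/(0.70 + 0.30 × 0.3) = 0.93/0.79 = 1.18. With the same shares and an 8 mm Hg difference, H3 shifts by 0.20 × 8 = 1.6 mm Hg. If p = c, the rate ratio is 1.00 and the H3 shift is zero.

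H2: no size is given. It would require the proportion of undiagnosed patients who meet NQF 0018, and the SAP does not say whether they are scored at all.

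**3. What does one indicator remove?**

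Suppose diagnosis alone drives the rate, with 15% vs 25% undiagnosed and an undiagnosed rate half the diagnosed rate. The unadjusted ratio is 0.925/0.875 = 1.06. Within each diagnosis stratum the rates are equal, so the indicator returns 1.00; a Poisson simulation gave the same.

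Now suppose the mix of branches 1 and 2 differs as well. Assume branch rates of 0.6, 0.3 and 0.2, with shares of 0.30, 0.55, 0.15 in pilot and 0.20, 0.55, 0.25 in control.

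- Unadjusted: (0.180 + 0.165 + 0.030)/(0.120 + 0.165 + 0.050) = 0.375/0.335 = 1.12.
- Among diagnosed patients alone: (0.345/0.85)/(0.285/0.75) = 0.406/0.380 = 1.07. This remains after conditioning on diagnosis; among undiagnosed patients the ratio is 1.00.
- Within each of the three branches the ratio is 1.00, so a three-level branch factor removes it.

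Simulated values were 1.13 unadjusted, 1.07 with the indicator and 1.01 with the three-level factor, which agrees apart from simulation error. This example ignores SBP matching, which would reduce the part due to branches 1 and 2.

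**The case against.** The strongest reply is that this is an added covariate, not an error. Every non-randomised comparison leaves variables out, and the SAP gives no evidence that the diagnosis mix differs or that diagnosis predicts outcome at equal SBP. The example pair shows only that discordant pairs are allowed, not that they lean one way. This stands, and it limits the point to low severity. What sets diagnosis apart from other unmatched variables is that the SAP itself uses it to define the branches and must extract it to establish eligibility.

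A second reply is that matching on the basis of the secondary criteria could mean pairing within branch. The explicit matching list contains neither branch nor diagnosis, so the natural reading is that controls must qualify for the secondary population, not that they must enter by the same branch.

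A third reply is that the time-0 description would reveal an imbalance. It might, but it names no variable and triggers no adjustment, and a term chosen after seeing the data is weaker than a pre-specified one.

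A reader might infer three stronger claims. None is supported:

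- That the secondary results will be biased in favour of RPM. No imbalance is shown, and the direction could be either.
- That H2 is distorted by a stated amount. The SAP does not say how undiagnosed patients are handled under NQF 0018.
- That one indicator settles all case-mix differences. It covers diagnosis, not the difference between branches 1 and 2.

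Read literally, the OR also applies the age, visit, insurance and exclusion criteria ("Not meet the exclusion criteria") to branch 1 only. Carry-over to all branches is probably intended; this is a wording clarification and not part of the point.

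**Conclusion.** The point holds for the secondary population only, as an inexpensive improvement of low severity. Diagnosis varies by construction there, and neither the matching nor the models address it. Whether bias follows depends on two things that the SAP does not show: a different diagnosis mix in pilot patients and matched controls, and a link between diagnosis and outcome at equal SBP. On the assumed inputs the effect is probably modest, with H1 the most exposed. The more extreme results need a 20-point imbalance, which is likewise an assumption. No primary-population analysis is touched.

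**What to change.** Pre-specify a yes/no indicator for hypertension diagnosis in the year before the start date in the secondary-population H1 and H3 models. State whether undiagnosed patients are scored on NQF 0018 and, if they are, add the indicator to H2 as well.

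Give branch 2 the same one-year diagnosis window. Otherwise a patient admitted through branch 2 on an older diagnosis alone would be coded as undiagnosed, and the indicator would disagree with the entry branch. The two readings of branch 2 admit different patients only where the sole diagnosis is more than one year old and the last BP is normal.

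If adjustment for the difference between branches 1 and 2 is also wanted, use a three-level entry-branch factor in place of the indicator.

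The cost is one term per model (two coefficients for the three-level factor), from data already needed for eligibility, plus a sentence each on the branch 2 window and on NQF 0018 scoring. The matching, the 2:1 ratio and all primary-population analyses stay as they are.

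### Antihypertensive treatment at time 0 is neither matched on nor included in the H1–H3 models, and H1 has no baseline covariate at all

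*SAP*

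**What the plan says.** - **Matching (SAP, Matching criteria).** There are five variables: sex, age within 5 years, "Mean SBP from T-365d to T-183d (+/- 10 mm Hg", "Mean SBP from T-182d to T-0d (+/- 10 mm Hg", and primary care use as "Number of office visits to primary care in the past year categories : 1, 2, 3-4, 5" or more. The RPM-enrolled comparison reuses these criteria at the time of ordering (SAP, RPM enrolled patient analyses).
- **Grouping (SAP, Hypothesis testing).** Groups are defined by clinic. H1, for example, states that intensification "will be greater in pilot clinic(s) with RPM compared to contemporaneous control clinic(s".
- **H1 outcome and model.** The outcome is listed as "Number of antihypertensive medication intensifications between the study start and the measure date". The model is Poisson, "otherwise negative binomial regression with study group as the independent variable". No other term is named.
- **H2 and H3 models.** H2 is analysed "using logistic regression with study group and baseline systolic blood pressure as independent variables" and H3 "using linear regression with study group and baseline systolic blood pressure as independent variables".
- **Time-0 description.** The SAP plans to describe the study and matched control populations at time 0. It does not list the characteristics and does not use them for adjustment.

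Medication appears only as the count of intensifications after study start. Treatment already in place at time 0 is not mentioned.

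**The concern.** Two patients with the same mean SBP, sex, age band and visit category match fully even if one takes no antihypertensive drug and the other takes several. Their prospects for a further intensification, and for a fall in SBP, may differ. SBP is measured under whatever treatment the patient receives, so matching on it does not make underlying severity equal.

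Three features of this plan make the omission worth correcting:

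1. Groups are formed by clinic. Prescribing practice tends to be shared within a clinic, so a difference between clinic groups does not average out as patients are added.
2. H1 counts changes to the regimen, so the starting regimen is an obvious candidate predictor. Yet H1 is the only one of the three models with no baseline covariate.
3. The secondary population pools patients without a hypertension diagnosis in the past year, diagnosed patients without two elevated readings, and the whole primary population (SAP, Groups of interest). Neither diagnosis nor treatment is a matching variable, so treatment at time 0 is likely to vary widely there.

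If treatment differs between the groups after matching, part of any H1 contrast could reflect where patients started rather than remote monitoring.

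**Working it through.** **Text check.**

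| Element | Terms stated | Treatment at time 0? |
|---|---|---|
| Matching list | sex, age, two SBP windows, visit category | no |
| H1 model | study group | no |
| H2 model | study group, baseline SBP | no |
| H3 model | study group, baseline SBP | no |
| RPM-enrolled comparison | same matching criteria, analogous comparisons | no |

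The SAP states no sample size, effect size, intensification rate or treatment distribution. There is no figure of its own to reproduce, and every input below is an assumption.

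**H1 illustration with no true effect of monitoring.** Let a and b be the shares on three or more drug classes in the pilot and control groups. Let k be the intensification rate of those patients relative to patients on fewer classes, with the same stratum rates in both groups. The unadjusted rate ratio is then

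RR = (1 − a + a·k) / (1 − b + b·k).

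The values of k used are 0.33 (0.20 against 0.60 intensifications per patient over 6 months), 0.5 (0.25 against 0.50), 0.7 and 0.85.

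| Pilot a, control b | k = 0.33 | k = 0.5 | k = 0.7 | k = 0.85 |
|---|---|---|---|---|
| 25%, 35% | 1.087 | 1.061 | 1.034 | 1.016 |
| 20%, 40% | 1.182 | 1.125 | 1.068 | 1.032 |

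Worked cell: a = 0.25, b = 0.35, k = 0.5 gives (0.75 + 0.125) / (0.65 + 0.175) = 0.875 / 0.825 = 1.061.

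A 15-point imbalance (25% against 40%) gives 1.094 at k = 0.5 and 1.136 at k = 0.33. Equal shares give 1.00 for every k. Exchanging the two shares inverts the ratio: 1 / 1.016 = 0.98 and 1 / 1.182 = 0.85.

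**H3 illustration.** Spurious shift = imbalance in share × SBP difference by treatment that remains given baseline SBP. With an assumed 2 to 6 mmHg and imbalances of 5 to 20 points, the shift runs from 2 × 0.05 = 0.1 mmHg to 6 × 0.20 = 1.2 mmHg. No figure was computed for H2.

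**Limit of the illustration.** The formula uses the same stratum rates in both groups. If the group with more heavily treated patients also intensifies more readily, the two effects oppose each other. In the 1.061 scenario, control stratum rates 6.1% higher would bring the unadjusted ratio back to 1.061 / 1.061 = 1.00. Adjusting for class count would then show 1 / 1.061 = 0.94, which is the clinic-level difference that the adjustment cannot remove.

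**The case against.** The case against has real weight:

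- **A covariate can always be added.** This is a pilot study with five matching variables, two of them SBP windows, and diabetes or kidney function could be proposed in the same way. That is fair as a general caution. Treatment at time 0 differs from those examples because it is the starting state of the H1 outcome, and the SAP fixes the H1 model with no baseline term.
- **The assumed direction is not in the documents.** The SAP does not define intensification. If dose increases count, a patient on several drugs may have more, not fewer, ways to be intensified. An undiagnosed, untreated patient may be intensified less. This stands: k could exceed 1.
- **SBP already covers part of H2 and H3.** This also stands. Any remaining effect there should be smaller, and the H3 illustration is modest.
- **A class count does not remove clinic prescribing habits.** This stands as well. As the working shows, removing one of two opposing biases can leave more net bias.
- **The data source is not named.** That is true of the SAP. Still, recognising an intensification after study start requires knowing the regimen at study start, so the information is needed for H1 in any case.
- **Medication may already be in the baseline table.** That is possible, since the characteristics are not listed. Describing an imbalance does not adjust for it.

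A reader might infer that baseline treatment determines the outcomes, or that the plan is biased in favour of remote monitoring. The documents support neither. They give no treatment distribution, no intensification rates and no sign of which clinics treat more heavily. It would likewise go too far to treat patients on three or more classes as having resistant disease, because the SAP says nothing on that.

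**Conclusion.** The omission is confirmed on the text. In a non-randomised comparison of clinics, treatment at time 0 is controlled neither by matching nor by modelling. It matters most for H1, which measures a change in that treatment and has no baseline covariate. Baseline treatment plausibly influences H1 and, to a lesser degree, H2 and H3.

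The size and direction of any bias are unknown. With assumed imbalances of 10 to 20 points and k from 0.33 to 0.85, the null H1 rate ratio ranges from about 1.02 to 1.18, or from about 0.85 to 0.98 if the imbalance is reversed. The H3 shift is 0.1 to 1.2 mmHg on its own assumptions. All of these become zero if the groups are balanced. The point is that the plan can adopt a better model at low cost, not that its results are shown to be wrong. The change should be made before the outcome comparisons are run.

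**What to change.** 1. Derive the number of antihypertensive drug classes at time 0, grouped 0, 1, 2, 3+, from the medication data needed to count intensifications. For the RPM-enrolled comparison, derive it at the date of RPM ordering.
2. Report its distribution by group after matching, for the primary, secondary and RPM-enrolled comparisons.
3. Add it together with baseline SBP to the H1 model, and add it to the H2 and H3 models.
4. Leave the matching list unchanged, so that no patient is lost to an extra matching variable.
5. State that the class count ignores dose and does not remove clinic-level differences in prescribing, so residual confounding remains possible.

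The variable is fixed before follow-up begins, so including it does not adjust away an effect of monitoring. The cost is SAP wording, one more derived variable, and at most three degrees of freedom in H2 and H3 and four in H1 (three for class count, one for baseline SBP).
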